## 2 OBJECTIVES AND PARAMETERS

### 2.1 Objectives

The objectives of this study are to assess the repeated-dose safety, efficacy, PK, **CCI** profiles of CTAP101 Capsules, immediate-release (IR) calcifediol, high-dose cholecalciferol, and paricalcitol plus low-dose cholecalciferol in patients with secondary hyperparathyroidism (SHPT), stage 3 or 4 chronic kidney disease (CKD), and vitamin D insufficiency (VDI).

### 2.2 Endpoints

#### 2.2.1 Efficacy Endpoints

[figure not shown]
This study is descriptive and no primary or secondary efficacy endpoints are defined.

#### 2.2.2 Pharmacokinetic Endpoints

The following PK parameters will be calculated for observed and baseline (BL)-adjusted serum calcifediol (also known as 25-hydroxyvitamin D3 [25D3]) **CCI** concentrations using noncompartmental methods (data permitting), where additional parameters may be evaluated based on the concentration-time data:

1.  $C_{\max}$  – maximum concentration (including  $C_{\max}$  during a 24-hour interval [ $C_{\max,0-24h}$ ]);
2.  $T_{\max}$  – time of maximum concentration (including  $T_{\max}$  during a 24-hour interval [ $T_{\max,0-24h}$ ]);
3.  $AUC_{0-t}$  – area under the concentration-time curve (AUC) from time 0 to the last measurable time point;
4.  $AUC_{0-t}$  – AUC from time 0 to a fixed time point t. This will include the AUC from time 0 to 24 hours ( $AUC_{0-24h}$ ) for all dosing regimens and AUC from time 0 to 28 days ( $AUC_{0-28d}$ ) for the monthly dosing regimens only;
5.  $AUC_{0-56d}$  – AUC over the entire study period (56 days);
6.  $AUC_{\tau}$  – AUC during the dosing interval ( $\tau$ ), where  $\tau$  = 24 hours for the daily dosing regimens and  $\tau$  = 28 days for the monthly dosing regimens.  $AUC_{\tau}$  will only be calculated for the monthly dosing regimens if deemed appropriate;
7.  $AUC_{0-\infty}$  – AUC from time 0 extrapolated to infinity (paricalcitol only);
8.  $AUC_{\text{ext}}$  – percentage of  $AUC_{0-\infty}$  obtained by extrapolation (a diagnostic parameter calculated and listed in the data listing, but not included in the descriptive statistics) (paricalcitol only);
9.  $C_{\text{avg}}$  – average concentration over a dosing interval after multiple doses. For the monthly dosing regimens, average exposure may be calculated over a 24-hour interval ( $C_{\text{avg},24h} = AUC_{0-24h}/24$  hours), the entire dosing interval ( $C_{\text{avg},28d} = AUC_{0-28d}/28$  days), and/or over the entire study period ( $C_{\text{avg},56d} = AUC_{0-56d}/56$  days);

10.  $T_{ss}$  – predicted time to steady state (paricalcitol only);
11.  $\lambda_z$  – terminal elimination rate constant (paricalcitol only);
12.  $t_{1/2}$  – terminal elimination half-life (paricalcitol only);
13.  $CL/F$  – apparent clearance after extravascular administration (paricalcitol only);
14.  $CL_{ss}/F$  – apparent clearance after multiple extravascular administrations;
15.  $V_d/F$  – apparent volume of distribution after extravascular administration (paricalcitol only);
16.  $RA, C_{max}$  – accumulation ratio based on  $C_{max}$ ;
17.  $RA, AUC$  – accumulation ratio based on  $AUC$ ;
18.  $LF$  – linearity factor (paricalcitol only).

CCI

## 2.2.4 Safety Endpoints

The safety and tolerability of each study drug will be evaluated using the following parameters:

1. Adverse events (AEs);
2. Physical examinations;
3. Vital signs;
4. Clinical laboratory test results (hematology and serum chemistry);
5. Incidence of hypercalcemia and drug-related hyperphosphatemia.

### 3 STUDY DESIGN

#### 3.1 Number of Subjects

Approximately 160 subjects will be screened to enroll approximately 80 eligible subjects with approximately 20 subjects per treatment arm. After signing the informed consent form, prior to any study-related activities, each subject will be assigned a unique 7-digit subject identification number (SSSNNNN) which will be retained throughout the study and that will be unique across all sites. The number will consist of a 3-digit site number (SSS), followed by a 4-digit subject number (NNNN) at the applicable clinical site. Should a subject be withdrawn from the study, that subject's number will not be reassigned.

Randomization will be accomplished in blocks of 4 subjects in a 1:1:1:1 ratio, with subjects assigned to treatment with either CTAP101 Capsules, IR calcifediol, high-dose cholecalciferol, or paricalcitol plus low-dose cholecalciferol. Randomization will occur on Day 1 (Visit 4) provided that each subject is deemed eligible for enrollment based, in part, on laboratory assessments obtained at screening (Days -42 to -36, Visit 1). Laboratory assessments obtained at Days -7 to -1 (Visits 2-3) will not be considered in the determination of enrollment eligibility.

#### 3.2 Sample Size Considerations

The total sample size of approximately 80 subjects was based on practical, clinical considerations and is typical for such studies. No formal sample size estimation was performed.

#### 3.3 Study Design

This is a phase 4, single- or multi-center, open-label study to evaluate the comparative safety, efficacy, and PK and **CCI** profiles of CTAP101 Capsules, IR calcifediol, high-dose cholecalciferol, and paricalcitol plus low-dose cholecalciferol **CCI** in male and female subjects at least 18 years of age with stage 3 or 4 CKD and VDI. The study will be conducted at up to 3 sites within the United States. Subjects (approximately 20 per arm) will receive the following treatments:

- 1) CTAP101 Capsules (30 mcg/capsule), 60 mcg by the oral route, once daily for 56 days;
- 2) Calcifediol IR (266 mcg/capsule), 266 mcg by the oral route, on Days 1 and 29;
- 3) Cholecalciferol (50,000 IU/capsule), 300,000 International Units (IU) by the oral route (6 capsules), on Days 1 and 29; and,
- 4) Paricalcitol (1 mcg/capsule) plus cholecalciferol (800 IU/capsule), 1 or 2 mcg plus 800 IU by the oral route, once daily for 56 days.

After 4 weeks of treatment, subjects who are receiving paricalcitol will double the dose to 2 mcg plus cholecalciferol 800 IU once daily in the morning before breakfast if all of the following conditions are met: the plasma iPTH has not decreased by at least 30% from

pretreatment BL and remains above 70 pg/mL, corrected serum total calcium is <9.8 mg/dL, and serum phosphorus is <5.5 mg/dL. Subjects who are receiving CTAP101 Capsules, IR calcifediol, or cholecalciferol (300,000 IU) will not undergo upward dose titration.

Subjects will reduce the dose of study drug per the following schedule if any of the following conditions are met: plasma iPTH is confirmed to be <30 pg/mL, corrected serum total calcium is confirmed to be >10.3 mg/dL, or serum phosphorus is confirmed to be >5.5 mg/dL.

Dose reduction (if needed):

CTAP101: decrease to 30 mcg per day (from 60 mcg per day)

IR calcifediol: hold Day 29 dose

Cholecalciferol 300,000 IU: hold Day 29 dose

Paricalcitol: decrease dose to 1 mcg per day (from 2 mcg per day)

Cholecalciferol 800 IU will not be adjusted

Subjects will suspend dosing if plasma iPTH is confirmed to be <15 pg/mL or corrected serum total calcium is confirmed to be >11.0 mg/dL, and will resume dosing when plasma iPTH is  $\geq$ 30 pg/mL and corrected serum total calcium is <9.8 mg/dL per the following schedule. In the event that a dose reduction is required for a subject receiving the minimum dosage of CTAP101 Capsules (30 mcg per day) or paricalcitol (1 mcg per day), the subject will suspend dosing and resume when iPTH is  $\geq$ 30 pg/mL and corrected serum total calcium is <9.8 mg/dL at the same minimum dosage.

Dose resumption (if needed):

CTAP101: 30 mcg per day

Paricalcitol 1 mcg per day

The subjects will be housed in a phase 1 unit for approximately 14 to 26 hours at the beginning of the study and on study Day 29 to provide the blood samples required for a detailed determination of the PK profiles for serum calcifediol [REDACTED]

[REDACTED] Blood samples for some of the PK and [REDACTED] assessments will be collected in the phase 1 unit at -2, 0, 2, 4, 6, and 12 hours, either in the phase 1 unit or during an outpatient visit at 24 hours, during the outpatient visit at 48 hours, and then weekly following the first dose and the Day 29 dose of study drug. Blood samples for other [REDACTED] assessments will be collected at less frequent intervals. Urine collections (over 24 hours) will be obtained at pretreatment BL (Visits 2 and 3), starting immediately after dosing on Day 1 (Visit 4) and Day 29 (Visit 10), and at the end of study (EOS) visit

(Visit 16) or at early termination (ET). The full schedule of assessments is provided in Table 1.

Subjects receiving treatment with calcitriol or another 1 $\alpha$ -hydroxylated vitamin D analog, or if serum total 25D >30 ng/mL when taking vitamin D supplementation (including multivitamins and fish oil), will complete a 4-week washout period before BL assessments. Subjects will forgo further dosing with these nonstudy drugs for the duration of the study. Subjects receiving calcimimetic therapy within the 12 weeks preceding Screening will be ineligible for enrollment.

Blood samples will be collected from all subjects at weekly intervals during the screening and BL periods, during the 8-week treatment period, and at the specified times during the PK/CCI assessment. Key parameters to be analyzed in the collected samples include some or all of the following: serum calcifediol, CCI [REDACTED]

[REDACTED] serum 24,25D3, CCI [REDACTED]

Vitals signs and AEs will be monitored at each study visit. Other safety parameters to be monitored less frequently include CCI [REDACTED]

[REDACTED] brief physical examinations, and clinical laboratory tests (hematology and serum chemistry). The number and percentage of subjects with hypercalcemia (defined as 2 consecutive visits with serum total calcium >10.3 mg/dL) or hyperphosphatemia (defined as 2 consecutive visits with serum phosphorus >5.5 mg/dL) will be calculated as a secondary safety endpoint.

Subjects will maintain a dietary intake during the study of approximately 1,000 to 1,500 mg of elemental calcium per day with dietary counseling and, as necessary, administration of a daily calcium supplement.

**Table 1. Schedule of Assessments**

	Screening	Washout	Baseline		Treatment												EOS/ ET
Visit	1		2	3	4	5	6	7	8	9	10	11	12	13	14	15	16
Week	-5		-1	-1	1	1	1	2	3	4	5	5	5	6	7	8	9
Day(s)	-42 to -36	-35 to -8	-7 to -2	-1	1	2	3	8	15	22	29	30	31	36	43	50	57
Hour(s)					(GCRC)					(GCRC)							
CCI					-2, 0, 2, 4, 6, 12	24	48			-2, 0, 2, 4, 6, 12	24	48					

Abbreviations: 1,25D3, 1,25-dihydroxyvitamin D3; 24,25D3, 24,25-dihydroxyvitamin D3; CCI, 25-hydroxyvitamin D; 25D3, calcifediol; BMI, body mass index; CCI [REDACTED] eGFR, estimated glomerular filtration rate; EOS, end of study; ET, early termination; CCI [REDACTED] GCRC, general clinical research center; HIV, human immunodeficiency virus; CCI [REDACTED] ionized calcium; iPTH, intact parathyroid hormone; CCI [REDACTED]

NOTE: The number listed under each respective event reflects the number of occurrences for that specific type of event on the specific visit designations; absence of number designation indicates that no occurrence of such event is required.

a Study drug dispensing for subjects assigned to CTAP101 Capsules and paricalcitol capsules plus low-dose cholecalciferol.

b Study drug dispensed for t = 0 dose on Days 1 and 29 from monthly study drug supply.

CCI

d Partial chemistry panel includes serum calcium, calcium (corrected), phosphorus, and albumin.

CCI

## 4 GENERAL STATISTICAL CONSIDERATIONS

All analyses described in this plan are considered a priori analyses in that they have been defined before locking the database. All other analyses, if any, designed subsequent to locking the database will be considered post hoc analyses and will be applied as exploratory methodology. All post hoc analyses will be identified as such in the clinical study report.

All statistical tests will be tested at  $\alpha = 0.05$ , 2-sided significance level, unless otherwise stated. Descriptive statistics for continuous variables will include number of subjects, mean, standard deviation (SD), median, minimum, and maximum, unless otherwise noted. In descriptive summary tables of PK CCI data, if needed, the geometric mean, geometric percent coefficient of variation (CV%), and arithmetic CV% will be included, where the geometric mean will be calculated using the exponential function (exp) of the mean of the natural log (ln)-transformed data, the geometric CV% will be calculated as  $[\exp(\text{SD}^2)-1]^{1/2} \times 100$ , where SD is the standard deviation for ln-transformed data, and the CV% will be calculated as  $100 \times (\text{SD}/[\text{arithmetic mean}])$ . Descriptive statistics for categorical variables will consist of counts and percentages.

Arithmetic means, SDs, medians, and geometric means will be reported with the same number of significant figures as the reported values. Minimum and maximum values will be reported with the same accuracy as the reported source data. The CV% and geometric CV% will be rounded to 1 decimal place.

Denominators for percentage of subject calculations will be based on the number of subjects in the subgroup and selected population unless otherwise specified.

All analyses will be conducted with SAS® version 9.4 or later using procedures appropriate for the particular analysis.

## 5 ANALYSIS POPULATIONS

### 5.1 Intent-to-Treat Population

The intent-to-treat (ITT) population will include all subjects who are randomly assigned to treatment. If actual treatment differs from the randomized treatment, the randomized treatment will be used.

### 5.2 Per-Protocol Population

CCI

If actual treatment differs from the randomized treatment, additional analyses using the actual treatment may be provided.

### 5.3 Safety Population

The safety population will include all subjects who are randomly assigned to treatment and receive at least 1 dose of study drug. The safety population will be used for all safety assessments.

### 5.4 Pharmacokinetic Population

The PK population will include all subjects who are randomly assigned to treatment, receive at least 1 dose of study drug, have no major protocol deviations, have at least 1 PK data point at BL, and sufficient measureable serum calcifediol or paricalcitol concentrations to facilitate the calculation of at least 1 postdose PK parameter using validated methods. Presentation of data will use the actual treatment. In cases where a subject's dosing compliance is found to be an issue, PK parameters may not be calculated for that subject.

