5.2 Dosing Plan

Approximately 80 subjects will be randomized 1:1:1:1 (approximately 20 per arm) to receive one of the listed study medications with a sufficient quantity of a non-alcoholic beverage to enable swallowing of the capsules:

- 1) CTAP101 Capsules 60 mcg once daily outside of the phase 1 unit at bedtime, except on Days 1 and 29 when dosing will occur in the phase 1 unit in the morning before breakfast.
- 2) IR calcifediol 266 mcg in the phase 1 unit before breakfast on the mornings of Day 1 and Day 29.
- 3) Cholecalciferol 300,000 IU (high-dose) in the phase 1 unit before breakfast on the mornings of Day 1 and Day 29.

4) Paricalcitol 1 mcg plus cholecalciferol 800 IU (low-dose) once daily outside of the phase 1 unit in the morning before breakfast, except on Days 1 and 29 when dosing will occur in the phase 1 unit before breakfast.

After 4 weeks of treatment, subjects who are receiving paricalcitol will double the dose to 2 mcg plus cholecalciferol 800 IU once daily in the morning before breakfast provided that (a) the plasma iPTH has not decreased by at least 30% from pretreatment BL and remains above 70 pg/mL, (b) corrected serum calcium is <9.8 mg/dL, and (c) serum phosphorus is <5.5 mg/dL. Subjects who are receiving CTAP101 Capsules, IR calcifediol or cholecalciferol (300,000 IU) will not undergo upward dose titration.

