5.6 Treatment Compliance

Study treatment compliance will be assessed at all specified visits. The Investigator or assigned designee will perform drug accountability and dosing compliance calculations for all study drugs (number of capsules that should have been taken versus actual number taken as evidenced by written dosing records, subject dosing diaries, and the number of capsules remaining in bottles of study drug assigned to each subject). Dosing compliance at <80% or >120% should be reported as a protocol deviation.

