9.4 Analysis Populations

CCI

The safety population will include all subjects who are randomly assigned to treatment and receive at least 1 dose of study drug. CCI

The PK population will include all subjects who are randomly assigned to treatment, receive at least 1 dose of study drug, have no major protocol deviations, have at least 1 PK data point at BL, and sufficient measureable serum calcifediol or paricalcitol concentrations to facilitate the calculation of at least 1 postdose PK parameter using validated methods.

All planned analyses will be specified in an accompanying statistical analysis plan (SAP).

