10.8 Protocol Deviations

Protocol deviations are any intentional or unintentional change from an IRB approved protocol that are not approved by the IRB prior to initiation of the change and are collected in EDC.

Major protocol deviations are deviations that result in increased risk to subjects, affect the rights, safety, or welfare of the subjects or affect the integrity of the study.

Major protocol deviations may include but are not limited to deviations from the inclusion/exclusion criteria, informed consent deviations, concomitant medication restrictions, dosing non-compliance, and any other protocol requirement that results in a significant added risk to the subject or has an impact on the quality of the data collected or the outcome of the study.

The sponsor requires that all major protocol deviations be reported to the IRB. In addition, the Investigator is responsible for adhering to his/her IRB's protocol deviation reporting requirements.

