### 7.3 Statistical Analysis of Pharmacokinetic Parameters

As an exploratory analysis, PK parameters for observed and BL-adjusted serum calcifediol will be compared between treatments using a mixed-effects model for the PK population. The dependent variable will be the value of the PK parameter. The model will include a term for treatment and BL calcifediol as a covariate. The PK parameters

compared may include  $C_{max}$  and  $AUC_{0-24h}$  for Day 1 and  $C_{max}$ ,  $AUC_{0-24h}$  (ie,  $AUC_{tau}$  for daily dosing regimen), and  $C_{avg}$  for Day 29. Additional parameters (eg, alternative  $AUC_{0-t}$  parameters) may be compared (and/or substituted) as deemed appropriate.

[figure not shown]
Treatment least-squares means and least-squares differences and 95% confidence intervals for the difference will be constructed for the values of each parameter. In addition, the  $P$  values will be presented for treatment and BL in the analysis table.

The SAS Proc Mixed code is as follows:

[figure not shown]
```
PROC MIXED DATA = adpc;
  BY paramn paramcd param;
  CLASS trtp;
  MODEL aval = trtp base_calcifediol;
  ESTIMATE 'CTAP101 Capsules vs. Calcifediol IR' trtp 1 -1 0 0 / cl;
  ESTIMATE 'CTAP101 Capsules vs. Cholecalciferol' trtp 1 0 -1 0 / cl;
  ESTIMATE 'CTAP101 Capsules vs. Paracalcitol plus cholecalciferol' trtp 1 0 0 -1 / cl;
  RUN;
```

[figure not shown]
Alternative statistical analyses may be provided if insufficient data or issues with the model are found.

CCI

CCI

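### The compliance exclusion in the PK population acts on the whole subject rather than on the affected profile, so it can discard valid Day 1 CTAP101 data and tilt the Day 29 comparison with the two monthly arms

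*SAP*

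**What the plan says.** Two routes lead from non-compliance to loss of PK data.

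- **Population route.** Protocol 9.4 requires PK-population subjects to "have no major protocol deviations, have at least 1 PK data point at BL", and SAP 5.4 repeats the deviation condition. Protocol 10.8, in its list of what major deviations may include, names "informed consent deviations, concomitant medication restrictions, dosing non-compliance".
- **Parameter route.** SAP 5.4 alone adds that where a subject's "dosing compliance is found to be an issue, PK parameters may not be calculated for that subject".

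The only numerical limit is in protocol 5.6: "Dosing compliance at <80% or >120% should be reported as a protocol deviation". It is not said to be a major deviation, and SAP 5.4 does not refer to it.

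On dosing, protocol 5.2 gives "CTAP101 Capsules 60 mcg once daily outside of the phase 1 unit at bedtime, except on Days 1 and 29". Paricalcitol plus low-dose cholecalciferol is also taken daily at home apart from those two days. IR calcifediol and high-dose cholecalciferol are given only in the unit, on Days 1 and 29. SAP 9.7 lists capsule-count compliance for the two daily arms, at visits that run to the end of the study.

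SAP 7.2 computes daily-arm parameters from the 24 hours after the Day 1 dose and the 24 hours after the Day 29 dose. Under SAP 7.3 the parameters "will be compared between treatments using a mixed-effects model for the PK population", with CTAP101 contrasted against each other arm.

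**The concern.** The exclusion is decided after randomisation, is triggered by behaviour that two of the four arms cannot show, and covers more data than that behaviour can affect. A subject who stops taking capsules at home in week 3 still has a sound Day 1 profile. A subject who lapses only after Day 29 has two sound profiles. As written, either could lose all PK parameters.

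Two of the three SAP 7.3 contrasts are at stake: CTAP101 against IR calcifediol and against high-dose cholecalciferol. In these, one side may be filtered on home adherence and the other cannot be. Protocol 3.2 names comparison of the regimens, and better description of their repeated-dose PK, among the principal aims. With about 20 subjects per arm, each discarded profile counts. With no criterion and no period stated, the decision is left to judgement in an open-label trial.

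**Working it through.** The plan has no figure to reproduce: SAP 3.2 states that no formal sample size estimation was done.

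**Inputs**
- 56 daily doses, of which 2 are in the unit (protocol 5.2, SAP 3.3). Home doses: Days 2-28 = 27 and Days 30-56 = 27, total 54. Monthly arms: 0 of 2 doses at home.
- Daily-arm windows of 24 h after the Day 1 and Day 29 doses (SAP 7.2).
- Half-life after repeat dosing about 30 days (protocol 3.2).
- About 20 subjects per arm (SAP 3.1).
- Non-compliance rate and degree: not in the documents. Assumed: 5% to 30% of the CTAP101 arm, taking 50% to 79% of home doses.

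**Step 1: which doses can affect which parameters.** The first scheduled CTAP101 home dose is at bedtime on Day 2, after the 24 h sample, so no home dose bears on the Day 1 parameters. The 27 home doses on Days 2-28 bear on the Day 29 parameters. The 27 on Days 30-56 bear on neither.

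**Step 2: why the period matters.** Take the protocol's 80% limit.
- All doses taken to Day 29, then 12 missed: 44/56 = 78.6% over the whole course. The subject is flagged, yet both profiles are sound.
- 11 missed on Days 2-28, none later: 45/56 = 80.4% over the whole course. The subject is not flagged, yet took only 17/28 = 60.7% of the doses before the Day 29 profile.
- Judged on Days 1-28 alone, 6 missed gives 22/28 = 78.6% and 5 missed gives 23/28 = 82.1%.

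**Step 3: Day 29 shift if under-takers are dropped.** The model is one-compartment accumulation with k = ln 2/30 per day, the Day 1 dose always taken, and missed doses spread evenly over the home days.

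- Accumulated amount before the Day 29 dose, in single doses: sum of exp(-kj) for j = 1 to 28 = 20.38. The Day 1 dose contributes exp(-28k) = 0.52 and the home doses 19.86.
- Relative exposure at adherence a: r = (0.52 + 19.86a)/20.38. So r(0.50) = 0.513 and r(0.79) = 0.795.
- Mean in adherers over mean in all treated, with fraction q excluded: 1/(1 - q + q r). Example: q = 0.10, a = 0.50 gives 1/(0.90 + 0.0513) = 1.051.

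**Step 4: precision.** The SE of a difference against a full arm is multiplied by sqrt((1/n + 1/20)/(2/20)). The difference detectable at 80% power is (1.960 + 0.842) x sqrt(1/n + 1/20), which is 0.89 SD at 20 v 20.

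| Excluded | n kept | Day 29 ratio (a = 0.79 to 0.50) | SE multiplier | Detectable difference |
|---|---|---|---|---|
| 5% | 19 | 1.01 to 1.03 | 1.013 | 0.90 SD |
| 10% | 18 | 1.02 to 1.05 | 1.027 | 0.91 SD |
| 20% | 16 | 1.04 to 1.11 | 1.061 | 0.94 SD |
| 30% | 14 | 1.07 to 1.17 | 1.102 | 0.98 SD |

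Counting the Day 29 unit dose, taken by everyone, lowers the home share from 19.86/20.38 = 97% to 19.86/21.38 = 93%, which shrinks the ratios slightly. For Day 1, later adherence leaves the values unchanged; the cost is lost subjects and weaker randomised comparability.

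**The case against.** Much of the opposing case stands, and it limits the claim.

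- **Removal is not mandated.** A reader might infer that non-compliance erases a subject's whole PK record. The documents do not say so. SAP 5.4 is permissive, protocol 10.8 only says what major deviations may include, and protocol 5.6 does not call its limit major. The SAP 5.4 sentence concerns parameters, not concentrations. Excluded data stay in the listings (SAP 5.5), and the protocol plans ITT descriptions of serum calcifediol.
- **The monthly arms are not unselected.** They pass the same deviation and data-sufficiency filters. Protocol 5.6 asks for compliance calculations for all study drugs, and one missed monthly dose is 1 of 2, or 50%. They escape only selection on home adherence.
- **The direction is not fixed.** Dropping subjects above 120% would lower the CTAP101 mean.
- **Adherer-only Day 29 PK is a legitimate target.** Clearance and accumulation ratios presuppose that the labelled doses were taken.
- **Compliance on Days 30-56 is not irrelevant to all PK output.** Weekly concentrations after Day 29 are summarised in the PK population (SAP 7.1) and do depend on it.
- **Edge cases.** An unscheduled home dose after discharge at 12 h could affect the 24 h sample. In the paricalcitol arm the Day 2 morning dose falls at about 24 h.
- **Who classifies deviations.** SAP 6.2 says the coordinator logs major deviations. It does not support the inference that the coordinator decides which are major. The PP definition is redacted, so a compliance limit there cannot be ruled out.

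None of this supplies a reason to drop Day 1 parameters for later lapses, or to let lapses after Day 29 void Day 29 parameters.

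**Conclusion.** The concern holds in limited form. The compliance rules are written per subject, with no stated criterion or period and no exemption for Day 1. They can discard valid Day 1 CTAP101 profiles. Where under-takers are dropped, they raise the Day 29 CTAP101 mean relative to the two monthly arms.

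The size is unknown, because the documents give no non-compliance rate. Under the stated assumptions it is about 1% to 5% on baseline-adjusted values with 5% to 10% of the arm excluded, and up to 17% at 30% excluded and 50% adherence. On observed values the percentage is smaller, because the baseline is retained. The loss of precision is small: 1% to 3% on the SE at the lower rates.

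The SAP 7.3 comparison is exploratory and no efficacy endpoint is defined, so this does not undermine the trial. It is a cheap improvement worth making before lock.

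A related inconsistency needs settling anyway. SAP 7.2 puts every PK-population subject in the parameter summaries, while SAP 5.4 allows parameters to be withheld from some of them.

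**What to change.** In SAP 5.4, replace the sentence that lets parameters be withheld for the subject with exclusions by profile:

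1. **Day 1 parameters:** keep for all dosed subjects with an evaluable profile, whatever their later compliance.
2. **Day 29 parameters, daily arms:** judge on compliance over Days 1-28 only, with a criterion fixed before lock, for example the protocol's <80% or >120%.
3. **Compliance on Days 30-56:** apply only to the concentration summaries after Day 29.
4. **Population rule:** state that dosing non-compliance alone is handled by items 1 to 3 and not by removal from the PK population. Align protocol 9.4 or record the difference.
5. **SAP 7.2:** reword so that it agrees with 5.4 on who enters the parameter summaries.
6. **Reporting:** keep the compliant-subject Day 29 analysis, add the SAP 7.3 contrasts in all dosed subjects with evaluable profiles as a sensitivity analysis, and tabulate exclusions by arm and reason.

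The cost is SAP wording and one further run of the 7.3 table. The all-dosed Day 29 CTAP101 result may be slightly lower and more variable. No trial procedure changes.
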